Dosing strategies for de novo once-daily extended release tacrolimus (LCPT) in kidney transplant recipients

NCT Number: 03713645

Date: August 21, 2018

1) Abstract of the study

Outcomes after kidney transplantation have been significantly enhanced with the advances made in immunosuppressive therapies. Tacrolimus is currently marketed as an extended-release once-daily formulation dosing option for patients, decreasing pill burden and possibly decreasing adverse effects. Some transplant recipients have been shown to have higher dosage requirements. According to the literature, this can be linked to genetic disparities in the metabolism of tacrolimus.. This potential complication, where differences on specific genes alters metabolism of tacrolimus, can increase difficulty in getting to a therapeutic drug level for immunosuppressants and is one large factor that contributes to the fact that kidney transplant survival rates differ between patients. Due to the enhanced bioavailability of MeltDose formulation once-daily extended-release tacrolimus, its de novo use in recent research and practice has been shown to expedite achievement of target tacrolimus trough concentrations. De novo use of once-daily tacrolimus formulations is understudied. Through a prospective investigational study, we aim to determine the optimal strategy for de novo dosing of once-daily extended release tacrolimus (MeltDose formulation) for kidney transplant recipients at Temple University Hospital.

2) Protocol Title

Dosing strategies for de novo once-daily extended release tacrolimus (LCPT) in kidney transplant recipients

3) Investigator(s)

Principal Investigator(s): [name]. BCPS

Co-PI: [name] [name], CM, FACS, FRCSC

4) Objectives

Primary Objectives:

Identify the target dose of de novo once-daily MeltDose formulation of tacrolimus that achieves therapeutic tacrolimus trough concentrations for kidney transplant patients at Temple University Hospital

Secondary Objectives:

Identify the time to achievement of therapeutic trough concentrations for the de novo MeltDose formulation of tacrolimus

Identify if the CYP3A5 genetic allele is expressed in enrolled participants to retrospectively determine correlation between CYP3A5 genotype expression and other factors (e.g., time to trough, tacrolimus dosing, patient outcomes, demographics) in kidney transplant patients

5) Rationale and Significance

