Tacrolimus is the most commonly utilized calcineurin inhibitor after kidney transplantation. It is used in combination with mycophenolate mofetil and prednisone in order to provide sufficient immunosuppression to prevent acute rejection of transplanted organs. The development of a MeltDose tablet formulation has been designed to enhance the bioavailability of tacrolimus due to the low water solubility of the drug. In clinical trials, the utilization of MeltDose tablet formulations of tacrolimus has been shown to provide rapid achievement of target tacrolimus trough concentrations. This once daily dosing regimen has also led to lower peak concentrations and equivalent overall exposure when compared to immediate release and other extended release formulations of tacrolimus. Similar efficacy and safety profiles have been demonstrated when comparing the MeltDose formulation of tacrolimus to other available formulations.

Some transplant recipients have been shown to metabolize tacrolimus at a higher or lower rate compared to other patients, which can greatly impact post-transplant outcomes. This can be prompted by the patient having polymorphisms of the cytochrome P450 3A5 (CYP3A5) gene that they may possess more so compared to others. If a patient is a CYP3A5*1 allele expressor, this leads to metabolically active CYP3A5 causing higher metabolism rates of tacrolimus. CYP3A5 expressors can require up to 2-fold higher tacrolimus doses to achieve similar trough concentrations compared to CYP3A5 non-expressors. This sparks the question as to what the optimal initial dosing of the MeltDose formulation of tacrolimus should be when used in the *de novo* setting for kidney transplant patients. Delayed achievement of target tacrolimus trough concentrations has been linked to higher rates of acute rejection as well as development of *de novo* donor-specific antibodies. Avoiding subtherapeutic and supratherapeutic concentrations of tacrolimus in the early post-transplant period will help to lower risk for acute rejection.

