demographic information, comorbidities related to transplant, cause of kidney disease, incidence and severity of tremors, study drug dosing, other immunosuppressants prescribed, relevant labs (e.g., Cr, K, eGFR, HbA1c, blood glucose, tacrolimus level) and all other pertinent prospective data (e.g., rejection episodes). Only prospective data created between Day 0-Day 30 visit will be collected for the purpose of this research—no retrospective data will be collected. All PHI will be removed from this dataset and subjects will be assigned an arbitrary study ID number. This de-identified dataset will be kept in a separate locked drawer and locked office accessible to only research staff and entered into encrypted password-protected online database, Research Electronic Data Capture (REDCap™, ©Vanderbilt University). Access to REDCAP™ will be granted to [name], BCPS, [name], BA, BSN, RN, [name], and [name] MD, CM, FACS, FRCSC. Documents containing personal health information (e.g., consent, HIPAA form) will be kept in a separate locked drawer in a locked office accessible only to study investigators. Raw data will be exported into a password-protected Excel data sheet stored on Temple hospital computer in a locked research space for data analysis.

Data analysis will be performed by study staff with the assistance of a hospital appointed statistician. From REDCap, raw data will be exported into an Excel sheet and analyzed in SPSS®, version 21.0 for Windows (SPSS, Inc., Chicago, IL). Continuous data such as baseline demographics and laboratory values that are normally distributed will be presented as mean (SD) and non-normally distributed data as median (25-75% interquartile range). Other baseline characteristics and outcomes will be analyzed with the following tests: Chi-square or Fisher's exact tests for categorical data, and Student's T-tests or Mann-Whitney U tests for continuous data. Kaplan Meier statistical testing will be utilized to evaluate time to therapeutic trough concentration. Subgroup analysis stratified by CYP3A5 genotype will be performed. All tests will be two-tailed, and p-values < 0.05 will be considered statistically significant.

e) Withdrawal of Subjects

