Participants are volunteers and will be permitted to withdraw at any time during the duration of the study. Each participant will be made aware of the eligibility to withdraw at any time at the sole discretion of the participant. Participants will remain eligible for study participation even if they do not want to complete the saliva collection kit to determine CYP3A5 genotype. If this occurs we will write a note to file and not obtain their saliva sample. As volunteers, participants are not required to do any aspect of the study that they do not want to do. The participant will be withdrawn from the study only if they contact the Principal Investigator by phone or mail to decline further study participation. If notification of withdrawal is obtained from a subject, data collection on this subject will cease immediately and no data already collected will be utilized in data analysis.

f) Privacy & Confidentiality

Each participant will be made aware of rules and regulations regarding protected health information (PHI) as outlined under HIPAA. HIPAA authorizations will be obtained from each participant at the beginning of the study. All study staff and investigators will be CITI trained and receive training regarding HIPAA authorizations and the storage and protection of PHI. The information collected from each chart will be de-identified and assigned an arbitrary number. The dataset only with corresponding arbitrary number will be accessible only to study investigators within REDCap and in the form of a password-protected excel sheet. Consents, HIPAA form, and any other original copies with PHI will be stored in a locked separate drawer in a locked room accessible only to research staff. All saliva collection kits will be deidentified before being sent to the lab for genetic testing. Results of genetic testing will not be recorded into their chart, and will be used for research purposes only. Genetic testing results will not be shared with participants. The protected health information will not be reused or disclosed to

any other person or entity, except as required by law, for authorized oversight of the research study, or for other research for which the use or disclosure of the protected health information would be permitted.

9) Risks to Subjects

The use of tacrolimus extended-release de novo for the investigational purpose of conducting this research study will not involve more than minimal risk to the patient.

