***Dosing strategies for de novo once-daily extended release tacrolimus (LCPT) in kidney transplant recipients***

**NCT Number: 03713645**

**Date: August 21, 2018**

Descriptive statistics were used to characterize the baseline demographics of the entire cohort (intent to treat population). Continuous parametric data are presented as mean  $\pm$  standard deviation while continuous non-parametric data are presented as median (25%-75% interquartile range). Analysis of outcomes according to CYP3A5 expresser status within the modified ITT population were completed using the Kruskal-Wallis or ANOVA test for continuous data and the chi-squared test for categorical data. Tests were corrected for multiple comparisons as necessary utilizing the Bonferroni method. All tests were two-tailed, and  $p < 0.05$  was used to represent statistical significance. Time to therapeutic tacrolimus trough concentration was analyzed using a Kaplan-Meier time-to-event analysis. All analyses were performed using SPSS, version 26 for windows (Armonk, NY; IBM Inc.).

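### Protocol 8(e) bars from analysis all data already collected on anyone who formally withdraws, including attainments, time at risk, doses and safety data that the planned analyses could use

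*Protocol*

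**What the plan says.** Protocol 8(e), Withdrawal of Subjects, states the rule: on notice of withdrawal, "data collection on this subject will cease immediately and no data already collected will be utilized in data analysis". The trigger is narrow: "The participant will be withdrawn from the study only if they contact the Principal Investigator by phone or mail to decline further study participation". The same section lets participants decline the saliva kit, or any other element, and stay in. It does not name stopping the drug or missing visits as withdrawal.

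The analyses that would use the barred data are these:

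- **Time to target.** Protocol 8(d): "Kaplan Meier statistical testing will be utilized to evaluate time to therapeutic trough concentration". The SAP: "Time to therapeutic tacrolimus trough concentration was analyzed using a Kaplan-Meier time-to-event analysis". Neither gives a censoring rule.
- **Primary objective.** Protocol section 4: "Identify the target dose of de novo once-daily MeltDose formulation of tacrolimus that achieves therapeutic tacrolimus trough concentrations".
- **Safety.** Protocol 8(d) lists, among the data collected, laboratory values and "all other pertinent prospective data (e.g., rejection episodes"). Protocol 8(c) plans an interim look at efficacy and safety after the first 35 subjects, with a further 35 if required.
- **Populations.** The SAP uses descriptive statistics to "characterize the baseline demographics of the entire cohort (intent to treat population"), and analyses outcomes by CYP3A5 status in a modified ITT population. It defines neither population. It neither repeats nor overrides 8(e).

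**The concern.** Under 8(e), whether a participant is analysed depends on something that happens after enrolment. Someone who reached target on day 6 and withdrew on day 25 has a fully observed time to target and dose at target, yet both are removed. Someone who withdrew on day 6 without attaining has six days at risk that Kaplan-Meier can use by censoring. Those days are removed too.

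If those who leave differ in attainment, dose need or tolerability from those who stay, the remaining sample no longer represents the people who started the drug. Removing non-attainers makes attainment look faster, and removing attainers makes it look slower. The interim evaluation would omit any rejection episode or laboratory value seen before withdrawal. With 35 subjects, each person removed is 1/35 = 2.9% of the cohort.

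**Working it through.** The documents give no withdrawal, attainment or rejection rate, so there is no plan figure to reproduce. Every rate below is an assumption, except 35 subjects, 30 days of follow-up and the up-to-2-fold dose ratio, which come from the protocol.

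**Set-up.** Time to target is exponential with L = ln(4)/10 = 0.1386 per day, so true day-10 attainment is 75%.

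**(a) Withdrawal only before target, otherwise unrelated to prognosis.** Let m be the constant withdrawal hazard while below target, solved from w = [m/(L+m)](1 − exp(−30(L+m))), where w is the proportion withdrawing. The estimate after exclusion is [L/(L+m)](1 − exp(−10(L+m)))/(1 − w).

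| w | m per day | Numerator | Exclusion estimate | Bias (points) |
|---|---|---|---|---|
| 3% | 0.00435 | 0.7375 | 0.7375/0.97 = 76.0% | +1.0 |
| 6% | 0.00896 | 0.7246 | 0.7246/0.94 = 77.1% | +2.1 |
| 12% | 0.01910 | 0.6974 | 0.6974/0.88 = 79.2% | +4.2 |

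Censoring at withdrawal gives 75.0% in each row, because withdrawal here is non-informative given time at risk.

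**(b) Only slow attainers withdraw, before target.** Here censoring is no longer unbiased. Overall day-10 attainment stays at 75%. The share of bias removed is 1 − (censoring bias)/(exclusion bias).

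| Slow group | w | Exclusion | Censoring | Share removed |
|---|---|---|---|---|
| 40% of cohort, half the rate | 3% | 76.49% | 75.23% | 1 − 0.23/1.49 = 85% |
| | 6% | 78.00% | 75.49% | 1 − 0.49/3.00 = 84% |
| | 12% | 80.98% | 76.16% | 1 − 1.16/5.98 = 81% |
| 20% of cohort, quarter the rate | 3% | 76.96% | 75.42% | 1 − 0.42/1.96 = 79% |
| | 6% | 78.97% | 75.94% | 1 − 0.94/3.97 = 76% |
| | 12% | 82.90% | 77.69% | 1 − 2.69/7.90 = 66% |

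With one-decimal inputs the top figure reads 87% (1 − 0.2/1.5), which is rounding.

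**(c) Withdrawal only after target.** With 1, 2 or 4 of 35 withdrawing, exclusion gives a bias of −0.3, −0.6 or −1.3 points. Censoring gives none.

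**(d) Withdrawal unrelated to outcome, on average 4 of 35, spread over 30 days (simulation).** There is no bias. The SD of the day-10 estimate is 7.40 points with no withdrawal, 7.87 under exclusion (7.87/7.40 = 1.06) and 7.51 under censoring (1.015). About 3 observed attainments are barred.

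**Bounds when data stay excluded.** Suppose 4 of 35 are removed and 22 of the remaining 31 attained (71.0%). The all-enrolled figure then lies between 22/35 = 62.9% and 26/35 = 74.3%.

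**Dose.** Protocol section 5 says "CYP3A5 expressors can require up to 2-fold higher tacrolimus doses to achieve similar trough concentrations compared to CYP3A5 non-expressors". Suppose 14 of 35 are expressors who need twice the dose. The pooled mean relative dose is (14×2 + 21)/35 = 1.40. Removing two expressors gives (12×2 + 21)/33 = 1.36 (−2.6%). Removing two non-expressors gives (14×2 + 19)/33 = 1.42 (+1.7%).

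**Safety (chosen numbers).** With 3/35 = 8.6% rejections, removing two participants, one of whom had an episode, leaves 2/33 = 6.1%.

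**The case against.** The strongest reply is about size. The trigger is formal notice only, follow-up is about 30 days, laboratory monitoring matches routine care, and participants may refuse any element and stay. Few formal withdrawals are therefore likely, although that is an inference. The larger biases need about 4 of 35 to withdraw before target. In case (a) at 12%, 47% of those withdrawals fall by day 4 and 67% by day 7, within days of surgery and around an average stay of 4 days. One early withdrawal in 35 moves the estimate by about 1 point, against an SD of 7.4. Withdrawals before and after target also pull in opposite directions. All of this stands, and it limits the severity.

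The dose example uses a pooled mean that neither document plans. Within genotype the assumed means stay at 2.0 and 1.0, so the example shows a shift in case mix and nothing more. The rejection example is chosen, not derived, and the documents set no rejection threshold. Both objections stand.

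A reader might infer that 8(e) and the SAP flatly contradict each other. The documents do not support that. On its plain reading, an entire cohort includes those who withdrew, but the SAP never defines membership and could mean everyone analysable. It is an unresolved inconsistency, not two opposing rules.

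The rule may also be a deliberate promise to volunteers. The consent form is not in the public documents, so this cannot be checked, and the fix has to respect it. The SAP is dated 2018 but written in the past tense, so the analysis may already be done.

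None of this restores the barred data or gives an analytic reason for barring them.

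**Conclusion.** The rule is explicit and has no exception. If it is followed as written, observed attainments, time at risk, doses at target and safety data are lost for every formal withdrawal. How much this matters cannot be known from the documents. It is nil with no formal withdrawals, and a loss of precision only (about 6% in SD with 4 of 35) if withdrawal is unrelated to outcome. If withdrawal is related to outcome, there is bias in either direction. Under the assumed 75% day-10 attainment it is about +1 point at 3% and +4 points at 12% withdrawing before target, more if only slow attainers leave, and up to about −1.3 points for 4 of 35 leaving after target.

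Two stronger readings should be resisted. The documents do not show that the result is biased, or that attainment will look faster, because they say nothing about who withdraws or when. Nor is censoring a complete cure: it removes all the bias when withdrawal is non-informative, but about two thirds to 85% in the informative scenarios tried, which is why bounds are needed. Outcomes after withdrawal are unknown under any rule.

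This is a cheap improvement of low to moderate severity.

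**What to change.** **Protocol 8(e).** Amend it along these lines: *Collection of data stops at withdrawal. Data collected up to that date are retained and analysed unless the participant asks for their removal.* Match the consent wording. Apply the change to those already enrolled only as their consent permits.

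**SAP.** Define the ITT and modified ITT populations, and include withdrawn participants in the ITT cohort. Censor time to therapeutic trough at the last trough before withdrawal. Because censoring assumes non-informative withdrawal, add bounds that count withdrawn non-attainers first as all attaining and then as none attaining.

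**Where data must stay excluded, or enrolment is complete.** Report the number and timing of exclusions, with bounds, at the interim and final analyses.

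**Cost.** Protocol, consent and SAP amendments with IRB review, plus a little extra analysis. No extra patients, visits or samples are needed. If enrolment is over, only the reporting step remains.

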***Dosing strategies for de novo once-daily extended release tacrolimus (LCPT) in kidney transplant recipients***

**NCT Number: 03713645**

**Date: August 21, 2018**

Descriptive statistics were used to characterize the baseline demographics of the entire cohort (intent to treat population). Continuous parametric data are presented as mean  $\pm$  standard deviation while continuous non-parametric data are presented as median (25%-75% interquartile range). Analysis of outcomes according to CYP3A5 expresser status within the modified ITT population were completed using the Kruskal-Wallis or ANOVA test for continuous data and the chi-squared test for categorical data. Tests were corrected for multiple comparisons as necessary utilizing the Bonferroni method. All tests were two-tailed, and  $p < 0.05$  was used to represent statistical significance. Time to therapeutic tacrolimus trough concentration was analyzed using a Kaplan-Meier time-to-event analysis. All analyses were performed using SPSS, version 26 for windows (Armonk, NY; IBM Inc.).

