- All kidney transplant recipients at Temple University Hospital will receive a *de novo* combination maintenance immunosuppression regimen. This combination regimen includes **tacrolimus extended-release** and mycophenolate mofetil with or without prednisone. Mycophenolate mofetil and prednisone are started on the day of transplantation. The day of initiation of tacrolimus extended-release is decided per transplant surgeon discretion. **The use of tacrolimus extended-release *de novo* differs from the standard of care. Goal tacrolimus trough concentrations for tacrolimus extended-release are identical to the way that goal tacrolimus trough concentrations are drawn for tacrolimus immediate-release at Temple.** Upon hospital discharge after transplant surgery, patients will be seen in the outpatient abdominal transplant surgery clinic three times weekly. **Table B portrays the laboratory parameters that are drawn per research protocol which is identical to laboratory parameters drawn for all kidney transplant patients at Temple University Hospital (Refer to Table A).** Average length of inpatient stay is expected to be 4 days. Table 2 portrays the timeline of data collection. **The data collected that differs from standard of care includes the QUEST Tremor Questionnaire at Day 30 and the required oral swab for testing of CYP3A5 metabolic enzyme activity.**

Table B

Setting	Tacrolimus extended-release trough concentration	Serum creatinine	Glomerular filtration rate	Potassium	Blood glucose	Hemoglobin A1C
Day of Transplant		✓	✓	✓	✓	✓
Inpatient (lab parameters obtained every 24 hours; approximately)	✓ (once tacrolimus initiated)	✓	✓	✓	✓	

Days 0-4						
Outpatient (lab parameters obtained three times weekly on Mon, Wed, Fri; approx Days 4-30)	✓	✓	✓	✓	✓	

Table C

Day 0	Study drug (tacrolimus) initiated at 0.13/mg/kg/day for all patients (the day of initiation decided per transplant surgeon discretion)
Day 0-4	Inpatient laboratory parameters checked every 24 hours per Tables A and B
Day 4-30	Outpatient laboratory parameters checked three times weekly on Monday, Wednesday, and Friday per Tables A and B
Day 30 visit (+/- 5 days)	Draw tacrolimus trough levels, serum creatinine, estimated glomerular filtration rate, serum potassium, and blood glucose. Complete tremor questionnaire with participant.

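### All planned CYP3A5 comparisons are unadjusted; adding an adjusted dose ratio with a 95% CI would be a cheap improvement

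*SAP*

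**What the plan says.** The SAP is a single paragraph. For genotype it states: "Analysis of outcomes according to CYP3A5 expresser status within the modified ITT population were completed using the Kruskal-Wallis or ANOVA test". Those two tests serve continuous outcomes; categorical outcomes are compared by chi-squared. It adds "Tests were corrected for multiple comparisons as necessary utilizing the Bonferroni method", and for time to target "Time to therapeutic tacrolimus trough concentration was analyzed using a Kaplan-Meier time-to-event analysis".

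The Data analysis text in protocol section 8(d) lists Student's t or Mann-Whitney tests, chi-square or Fisher tests, Kaplan-Meier, and a subgroup analysis stratified by genotype. No covariate, regression model or confidence interval appears in either document.

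Four other places bear on the point:

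- Protocol section 6 (Investigational) gives tacrolimus "and mycophenolate mofetil with or without prednisone", so co-medication varies between patients.
- Protocol section 8(d) collects demographics and "other immunosuppressants prescribed", so age and prednisone use are on record. Weight is needed to compute the per-kg starting dose.
- The secondary objective in protocol section 4 sets out to correlate genotype with "time to trough, tacrolimus dosing, patient outcomes, demographics".
- The SAP says "Descriptive statistics were used to characterize the baseline demographics of the entire cohort", whereas the genotype comparison is made in a modified ITT population. It commits to no baseline table by genotype.

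**The concern.** Patients are not allocated to a genotype. If expressers and non-expressers differ in weight, age or prednisone use, and those factors affect the dose needed, an unadjusted test credits the whole dose difference to CYP3A5. Without a baseline table by genotype, a reader may be unable to tell whether this has happened.

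Even where the groups are balanced, variation in dose that recorded baseline data could explain stays in the error term of a study with 35 to 70 patients.

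Protocol section 5 says that expressers may need as much as twice the dose. The natural way to examine that statement is a dose ratio with an interval, and the named tests do not supply an interval.

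**Working it through.** The plan gives no power, SD or effect estimate for this comparison, so there is no figure to reproduce.

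**Inputs from the documents.** Enrolment is 35, with 35 more if required (protocol 8(c)). The starting dose is per kg and the same for all (section 6, Table C). The expected genotype effect is at most 2-fold (section 5). Research staff do not know genotype during the month (8(d), Data and Specimen Banking). Patients may decline the saliva sample (8(e)).

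**Assumed, because the documents are silent.** Two genotype groups, the covariate R², the size of any imbalance, the prednisone effect, and the spread of log dose.

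**1. Precision, covariates uncorrelated with genotype.** Let R² be the share of within-group variation in log dose that three covariates explain. The adjusted-to-unadjusted SE ratio is √[(1−R²)(n−2)/(n−5)].

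| R² | n = 35 | n = 70 |
|---|---|---|
| 0.1 | √(0.9×33/30) = 0.995 | √(0.9×68/65) = 0.970 |
| 0.2 | 0.938 | 0.915 |
| 0.3 | 0.877 | 0.856 |

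At n = 35 the SE falls about 6% at R² = 0.2 and 12% at R² = 0.3. Since 1/ratio² is 1/0.88 = 1.14 and 1/0.77 = 1.30, this is worth 14% and 30% more patients. At R² = 0.1 there is no material gain.

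**2. Where the gain shrinks.**

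- *Covariates associated with genotype.* Take mean weights of 80 and 90 kg, SD 20 kg and equal groups. The standardised difference is 0.5 and the variance inflation is 1 + 0.5²/4 = 1.0625. At n = 35 the ratios become √(0.99×1.0625) = 1.03 (R² = 0.1, a small loss) and √(0.88×1.0625) = 0.97 (R² = 0.2, a 3% gain).
- *Fewer genotyped patients.* At an assumed n = 25 the ratios are √(0.9×23/20) = 1.017 and √(0.8×23/20) = 0.959.

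**3. Possible bias.**

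- *Weight.* Mean weights of 80 and 90 kg, with dose need proportional to weight, give a spurious ratio of 90/80 = 1.125 if dose is analysed in mg. In mg/kg the same assumption gives 1.
- *Prednisone.* A 20-point gap in use with a 1.2-fold effect on dose need gives exp(0.2×ln 1.2) = 1.037.
- *Chance gaps.* With 50% prednisone use and 30-50% expressers, a gap above 20 points has probability 0.24-0.28 at n = 35 and 0.09-0.13 at n = 70 (normal approximation).

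**4. Simulation.** 3,000 runs per setting, half expressers, log dose in mg, residual SD 0.4, log-weight SD 0.22 with slope 1, age −0.08 per SD, prednisone 1.15-fold at 50% use. In the shifted rows expressers are 0.5 SD higher in weight and age and 10 points higher in prednisone use.

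| n | Shift | True ratio | Rejected, unadjusted | Rejected, adjusted |
|---|---|---|---|---|
| 35 | none | 1.0 | 0.046 | 0.044 |
| 70 | none | 1.0 | 0.048 | 0.051 |
| 35 | none | 1.5 | 0.690 | 0.788 |
| 35 | none | 2.0 | 0.989 | 0.996 |
| 35 | yes | 1.0 | 0.089 | 0.056 |
| 70 | yes | 1.0 | 0.116 | 0.056 |

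The expected bias in the shifted rows is 0.5×0.22 − 0.5×0.08 + 0.1×ln 1.15 = 0.110 − 0.040 + 0.014 = 0.084 in log dose. The simulated bias was 0.080 to 0.087, a ratio inflated by about 8-9%. Most of it comes through weight. In mg/kg the weight term drops out, leaving −0.026, a ratio of 0.974.

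**The case against.** A reader might infer that the genotype result does mix in weight, age and prednisone. The documents do not support that. Genotype is inherited, and research staff are unaware of it during the month, so neither these factors nor knowledge of the result can determine who is an expresser. Bias needs an association between them and genotype. The objective that lists demographics poses this as a question; it does not state that imbalance is expected. Optional prednisone is not confounding in itself. Without an association, the unadjusted test keeps its error rate (0.046-0.048 in the simulation).

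The other side has further points that stand in part:

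- The only dose that the documents set is per kg. If dose is analysed in mg/kg, a bias from weight proportional to dose need disappears. The unit is not stated, however, and later doses are titrated to trough.
- The protocol plans tests of baseline characteristics, and genotype is the only patient grouping that it names for analysis. The SAP's means or medians would let a reader form a crude dose ratio. What is still missing is an explicit baseline table by genotype and an interval for the ratio.
- Kruskal-Wallis or ANOVA with Bonferroni may mean more than two genotype groups. One ratio would then not be enough, and adjustment would cost more.
- This is a secondary objective, worded as a correlation. The unadjusted contrast describes what dose each group needed, which is a legitimate target. At a true 2-fold ratio, power is already high: 0.989 in the simulation, and 0.88-0.999 at n = 35 for log-dose SD 0.4-0.6 and 30-50% expressers.

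**Conclusion.** The point holds in a conditional form. Every named genotype comparison is unadjusted and none comes with an interval, although usable baseline covariates are collected or needed for dosing. The dose comparison may be confounded; it is not shown to be. In the one assumed scenario simulated, the ratio is inflated by 8-9% and type I error rises to 0.089-0.116, but that scenario analyses dose in mg and assumes half-SD shifts that the documents do not report.

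The precision gain is also conditional. It needs covariates that explain about 20% or more of log-dose variance. It is nil at 10% with 35 patients, and smaller if the covariates are related to genotype or fewer patients are genotyped. It matters mainly for genotype effects below 2-fold.

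This is a cheap improvement to a secondary analysis. The planned tests are not invalid.

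**What to change.** Add to the SAP a linear model of log dose on CYP3A5 status, adjusted for log weight, age and prednisone use (yes/no) at tacrolimus start. State the dose unit and the time point. Because log(mg/kg) = log(mg) − log(weight), including log weight makes the genotype coefficient the same in either unit. Report the adjusted dose ratio with its 95% CI, one for each genotype contrast if there are more than two groups, alongside the planned unadjusted test. Tabulate baseline characteristics by expresser status in the modified ITT population. The SAP is written in the past tense; if the analysis is already complete, label the model post hoc.

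The cost is some SAP wording, a few lines of code and about 3 degrees of freedom. Precision may fall slightly if the covariates explain little or the genotyped set is small. No new data are needed, provided that the weight used for dosing is kept.
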